**Appendix 4. Tanner Stages\***

1. Pubic hair (male and female)	
Tanner I	no pubic hair at all (prepubertal Dominic state)
Tanner II	small amount of long, downy hair with slight pigmentation at the base of the penis and scrotum (males) or on the labia majora (females)
Tanner III	hair becomes more coarse and curly, and begins to extend laterally
Tanner IV	adult-like hair quality, extending across pubis but sparing medial thighs
Tanner V	hair extends to medial surface of the thighs
2. Genitals (male) (One standard deviation around mean age)	
Tanner I	Testes, scrotum, and penis about same size and proportion as in early childhood
Tanner II	Enlargement of scrotum and testes; skin of scrotum reddens and changes in texture; little or no enlargement of penis (10.5-12.5)
Tanner III	Enlargement of penis, first mainly in length; further growth of testes and scrotum (11.5-14)
Tanner IV	Increased size of penis with growth in breadth and development of glans; further enlargement of testes and scrotum and increased darkening of scrotal skin (13.5-15)
Tanner V	Genitalia adult in size and shape
3. Breasts (female)	
Tanner I	no glandular tissue: areola follows the skin contours of the chest
Tanner II	breast bud forms, with small area of surrounding glandular tissue; areola begins to widen
Tanner III	breast begins to become more elevated, and extends beyond the borders of the areola, which continues to widen but remains in contour with surrounding breast
Tanner IV	increased breast size and elevation; areola and papilla form a secondary mound projecting from the contour of the surrounding breast
Tanner V	breast reaches final adult size; areola returns to contour of the surrounding breast, with a projecting central papilla.

\* Chart referenced from Marshall WA, Tanner JM, variations in the pattern of pubertal changes in boys and girls {34663}, {34664}

## **Appendix 5. Pregnancy Precautions, Definition for Female of Childbearing Potential, and Contraceptive Requirements**

### **1. Background**

Ribavirin is contraindicated in pregnancy as significant teratogenic and embryocidal effects have been demonstrated in all animal species tested. Pregnancy must be excluded before the start of treatment with study drugs and prevented thereafter by reliable contraceptive methods.

Pregnancy tests will be performed regularly throughout this study. Furthermore, RBV is known to accumulate intracellularly where it is cleared slowly, and is also excreted in semen. Therefore, extreme care must be taken to avoid pregnancy during RBV therapy and for up to 6 months following completion of treatment (7 months for males). Please refer to the latest version of the product insert for additional information.

Non-clinical toxicity studies of sofosbuvir demonstrated no adverse effect on fertility or embryo-fetal development. However, there are no clinical studies of sofosbuvir in pregnant women. Please refer to the latest version of the investigator's brochure for additional information.

### **2. Definition of Female of Childbearing Potential and Contraceptive Requirements for Female Subjects (and their male partners)**

For the purpose of this trial, all post-menarchal females will be considered to be of childbearing potential, unless there is documentation of irreversible ovarian failure or surgical sterilization.

Post menarchal females must have a negative serum pregnancy test at Screening and a negative urine pregnancy test on the Day 1 visit prior to dosing. They must also agree to one of the following from 3 weeks prior to Day 1 until 6 months after last dose of RBV:

- Complete abstinence from intercourse. Abstinence is an acceptable method of contraception only when it is in line with subject's preferred and usual lifestyle. Periodic abstinence (e.g., calendar, ovulation, symptothermal, post-ovulation methods) and withdrawal are not acceptable methods of contraception.

Or

- Consistent and correct use of 1 of the following methods of birth control listed below, in addition to a male partner who correctly uses a condom, from the date of Screening until 6 months after the last dose of RBV:
  - intrauterine device (IUD) with a failure rate of < 1% per year
  - female barrier method: cervical cap or diaphragm with spermicidal agent
  - tubal sterilization
  - vasectomy in male partner

- implants of levonorgestrel
- injectable progesterone
- oral contraceptives (either combined or progesterone only)
- contraceptive vaginal ring
- transdermal contraceptive patch

### **3. Contraceptive Requirements for Male Subjects (and their female partners)**

All male study participants must agree to consistently and correctly use a condom from Baseline until 7 months after the last dose of RBV. If their female partner is of childbearing potential (as defined above), their female partner must use 1 of the methods of birth control listed above from the date of Screening until 7 months after last dose of RBV.

Male subjects must agree to refrain from sperm donation for at least 7 months after the last dose of RBV.

### **4. Procedures to be Followed in the Event of Pregnancy**

Subjects will be instructed to notify the investigator if they become pregnant at any time during the study, or if they become pregnant within 6 months (7 months for partners of male subjects) of last RBV dose. Subjects who become pregnant or who suspect that they are pregnant must report the information to the investigator and discontinue study drug immediately. Subjects whose partner has become pregnant or suspects she is pregnant must report the information to the investigator.

Instructions for reporting pregnancy, partner pregnancy, and pregnancy outcome are outlined in Section [8.5.2.1](#).

ICH	International Conference on Harmonization (of Technical Requirements for Registration of Pharmaceuticals for Human Use)
LLT	lower level term
LLOQ	lower limit of quantitation
MedDRA	Medical Dictionary for Regulatory Activities
PK	pharmacokinetics
PT	preferred term
Q1	first quartile
Q3	third quartile
RBV	ribavirin
RNA	ribonucleic acid
SAE	serious adverse event
SAP	statistical analysis plan
SI (units)	International system of units
SOC	system organ class
SOF	Sofosbuvir (GS-7977)
SVR	sustained virologic response
SVRx	sustained virologic response x weeks after stopping study drug
TEAE	treatment-emergent adverse events

TFLs	tables, figures, and listings
ULN	upper limit of normal
WBC	white blood cell
WHO	World Health Organization

PHARMACOKINETIC ABBREVIATIONS AND DEFINITIONS

λ_z	terminal elimination rate constant, estimated by linear regression of the terminal elimination phase of the log plasma/serum concentration versus time curve of the drug
AUC	area under the plasma/serum concentration versus time curve
AUC _{tau}	area under the plasma/serum concentration versus time curve over the dosing interval
CL	systemic clearance of the drug after intravenous administration
CL/F	apparent oral clearance after administration of the drug: CL/F = Dose/AUC _{inf} , where “Dose” is the dose of the drug
C _{max}	maximum observed plasma/serum concentration of drug
C _{tau}	observed drug concentration at the end of the dosing interval
E _{max}	maximum (pharmacodynamic) effect
t _{1/2}	estimate of the terminal elimination half-life of the drug in serum/plasma, calculated by dividing the natural log of 2 by the terminal elimination rate constant (λ_z)
T _{max}	time (observed time point) of C _{max}

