**Evaluation Criteria:**

- Safety:** AEs, laboratory tests, physical examination, vital signs and Tanner Pubertal Stage assessments will be collected throughout the study.
- Efficacy:** Efficacy will be evaluated using scheduled assessments of HCV RNA performed using COBAS® AmpliPrep/COBAS® TaqMan® HCV Test.
- PK:** For subjects in the PK Lead-in, steady-state PK of SOF and its major metabolites GS-566500 and GS-331007 will be assessed at Day 7. For Cohorts 1 and 2, plasma samples will be collected for PK analyses following dosing of study drugs on Day 7 at the following time points: 0 (predose), 0.5, 1, 2, 3, 4, 8, and 12 hours postdose (with predose also serving as t= 24). For Cohort 3, plasma samples for PK analyses will be collected at the following time points: 0 (predose), 2, 4, 8, and 12 hours postdose (with predose also serving as t = 24). Plasma PK parameters such as Cmax, Tmax, Clast, Tlast, Ctau, AUCtau, and t1/2 will be estimated. For all subjects in the Treatment Phase, a single PK blood sample will be collected at all visits while on treatment. The PK of SOF, GS-566500 and GS-331007 and/or ribavirin will be assessed. The effect of age and SOF dose on PK (SOF and GS-331007) will be explored.

---

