- Obtain blood samples for the following laboratory analyses:
  - Hematology
  - Chemistry
  - Coagulation tests

- HCV RNA
- Viral sequencing (archive)
- Perform intensive PK sampling:
  - Blood samples will be collected at 0 (predose,  $\leq 30$  minutes prior to dosing). After collection of the predose sample, subjects will be provided a standardized meal. Within 5 minutes after consuming the standardized meal, subjects will be dosed with SOF + RBV per dosing requirements.
  - Post-dose blood samples will be collected as follows:
    - For Cohorts 1 and 2: 0.5, 1, 2, 3, 4, 8, and 12 hours post-dose (with predose also serving as  $t = 24$ ).
    - For Cohort 3 only: 2, 4, 8, and 12 hours post-dose (with predose also serving as  $t = 24$ ).
  - Subjects will be restricted from food intake until after collection of the 4-hour post dose blood sample, except for subjects in Cohort 3. Please also refer to the PK manual for details about standardized meals and PK sample processing instructions.

After completing the Day 7 intensive PK visit subjects will then continue to the Week 2 visit in Treatment Phase (described in Section 6.4.2) with no interruption in dosing.

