### 9.1.2. Primary Endpoints

For the PK Lead-in Phase, the appropriateness of the SOF dose will be assessed by evaluating the steady-state PK of the SOF and its metabolite GS-331007. The primary endpoint is  $AUC_{\tau}$  of GS-331007. Additional steady-state PK parameters of SOF and GS-331007 (e.g.,  $AUC_{last}$ ,  $C_{max}$ ,  $T_{max}$ ,  $C_{last}$ ,  $T_{last}$ ,  $C_{\tau}$ ,  $\lambda_z$ ,  $CL/F$ ,  $V_z/F$  and  $t_{1/2}$  and  $AUC_{\tau}$  of SOF) will be estimated and summarized as described in Section 9.4.

For Treatment Phase, the primary safety endpoint is any AE leading to permanent discontinuation of study drug (s). The key efficacy endpoint is SVR12.

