### **9.4. Pharmacokinetic Analysis**

PK analysis will be performed for PK Lead-in using the intensive PK analysis set. The concentration data of SOF and metabolites (GS-566500 and GS-331007) over sampling time will be listed and summarized by nominal time and cohort. Pharmacokinetic parameters (e.g.,  $AUC_{\tau}$ ,  $AUC_{last}$ ,  $C_{max}$ ,  $T_{max}$ ,  $C_{last}$ ,  $T_{last}$ ,  $C_{\tau}$ ,  $\lambda_z$ ,  $CL/F$ ,  $V_z/F$  and  $t_{1/2}$ ) will be listed and

summarized for SOF and metabolites (as applicable) using descriptive statistics (e.g., sample size, arithmetic mean, geometric mean and its 95% confidence interval, coefficient of variation %, standard deviation, median, Q1, Q3, minimum, and maximum) by cohort and overall. Plasma concentrations over time will be plotted in semilogarithmic and linear formats as mean  $\pm$  standard deviation, and median (Q1, Q3).

To evaluate the exposures of GS-331007 achieved in pediatric subjects of this study are similar to the exposures observed in adult subjects, GS-331007 exposure data from this study will be compared to the integrated adult data by carrying out an analysis of variance (ANOVA) for log-transformed  $AUC_{\tau}$  of GS-331007 as the primary endpoint while  $C_{\max}$  of GS-331007 as secondary endpoints. The 90% confidence intervals will be constructed for the ratio of geometric means of each PK parameters. The equivalence boundary is set as 50% to 200%. Individual patient management will be performed by maintaining exposures comparable to adults.  $AUC_{\tau}$  less than the 2.5th percentile of adult values may require dose adjustment as appropriate.

The effect of age and SOF dose on PK (SOF and GS-331007) will be assessed.

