1.2.1. PK Lead-in Phase

The PK Lead-in Phase will evaluate and/or confirm the age appropriate SOF dose by analyzing PK, safety, and antiviral activity of SOF + RBV through 7 days of dosing for each cohort.

Up to 10 genotype 2 or 3, treatment-naïve pediatric eligible subjects will be sequentially enrolled into each of the following 3 cohorts:

- Cohort 1: 12 to < 18 years old, weighing \geq 45kg
- Cohort 2: 6 to < 12 years old, weighing \geq 17kg and \leq 45kg
- Cohort 3: 3 to < 6 years old

The study will start with Cohort 1 where subjects will receive SOF (400 mg adult tablet or 4×100 mg tablets if determined necessary based on SOF swallowability assessment) + RBV for 7 days with intensive PK conducted on Day 7.

Cohort 2 subjects will receive 200 mg SOF (2×100 mg tablets or 4×50 mg capsules if determined necessary based on the SOF swallowability assessment) + RBV for 7 days with intensive PK conducted on Day 7.

Cohort 3 subjects weighing ≥ 17 kg will receive 200 mg SOF (4×50 mg capsules containing granules) + RBV for 7 days with intensive PK conducted on Day 7. Cohort 3 subjects weighing < 17 kg will receive 150 mg SOF (3×50 mg capsules containing granules) + RBV for 7 days with intensive PK conducted on Day 7.

Subjects enrolled in the PK Lead-in Phase will immediately enroll in the Treatment Phase as they completed Day 7 of the PK Lead-in Phase. Subjects continue dosing with SOF + RBV with no interruption of study drug administration.

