8. PHARMACOKINETIC ANALYSES

8.1. PK Analysis in PK Lead-in Phase (Intensive PK Analysis)

Intensive PK Analysis will be performed using PK Lead-in Phase Intensive PK Analysis Set. Concentrations of SOF and GS-331007 from subjects in the PK lead-in Phase over sampling time will be listed and summarized using descriptive statistics (n, arithmetic mean, geometric mean and its 95% confidence interval, coefficient of variation [%CV], SD, median, Q1, Q3, minimum, and maximum) by nominal time and cohort. For Cohorts 1 and 2, plasma samples will be collected for PK analyses following dosing of study drugs on Day 7 at the following time points: 0 (predose), 0.5, 1, 2, 3, 4, 8, and 12 hours postdose. For Cohort 3, plasma samples for PK analyses will be collected at the following time points: 0 (predose), 2, 4, 8, and 12 hours postdose. PK parameters from subjects in the PK lead-in Phase will be summarized (e.g; AUC_{τ} , AUC_{last} , C_{max} , T_{max} , C_{last} , T_{last} , C_{τ} , $T_{1/2}$, volume of distribution and clearance, as appropriate) by cohort.

To confirm the appropriateness of SOF dose for each age group, PK parameters for GS-331007 will be compared between each age group from this study and the SOF NDA patient population (which includes population-PK derived PK exposure data from adult phase 2 and 3 studies) by carrying out an analysis of variance (ANOVA) for log-transformed AUC_{τ} of GS-331007 as the primary endpoint and C_{max} of GS-331007 as a secondary endpoint. Geometric Mean Ratio and its 90% confidence interval will be provided.

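### The SAP's only definition of CL/F is the single-dose form Dose/AUCinf, which does not fit a plan whose only intensive PK profile is at steady state on Day 7

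*SAP*

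**What the plan says.** The SAP's Pharmacokinetic Abbreviations and Definitions gives CL/F as "apparent oral clearance after administration of the drug: CL/F = Dose/AUC", where the AUC carries the subscript inf and the dose is that of the drug. The same list defines AUCtau separately, as "area under the plasma/serum concentration versus time curve over the dosing interval". It has no entry for AUCinf, and the protocol glossary has none for CL/F.

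The intensive sampling is described as follows:

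- SAP 1.2.1 has each cohort take SOF + "RBV for 7 days with intensive PK conducted on Day 7".
- The protocol synopsis (Evaluation Criteria) says that "steady-state PK of SOF and its major metabolites GS-566500 and GS-331007 will be assessed at Day 7".
- Protocol 6.3.3 collects samples to 12 hours, "with predose also serving as" the 24-hour value. No intensive profile is scheduled on Day 1.

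The parameters are described as follows:

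- Protocol 9.1.2 lists CL/F and Vz/F under "Additional steady-state PK parameters of SOF and GS-331007".
- Protocol 9.4 lists CL/F with AUCtau and AUClast, to be "summarized for SOF and metabolites (as applicable) using descriptive statistics".
- SAP 8.1 names AUCtau and AUClast and then "volume of distribution and clearance, as appropriate", without a formula.

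AUCinf is absent from all three lists and from the list in the synopsis (Statistical Methods).

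**The concern.** Dose/AUCinf gives CL/F when the AUC follows a single dose. At steady state one dose is eliminated per dosing interval, so the matching expression is Dose/AUCtau. A Day 7 profile carried to infinity also contains what remains from the earlier doses. Dividing the dose by that larger area makes clearance look smaller than it is.

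A programmer who looks for the CL/F rule will find only the glossary line, and the Day 7 profile is the only one available to apply it to. At stake are the descriptive CL/F summaries by cohort and any volume derived from them. The bias depends on half-life and trough, so it need not be equal across cohorts and need not cancel when clearance is compared between ages. The tabulated CL/F would also differ from dose divided by the tabulated AUCtau.

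**Working it through.** The documents state no CL/F value, so there is no figure to reproduce. The check is on direction and possible size.

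**Inputs from the documents.** The dosing interval tau is 24 h. GS-331007 means come from Protocol Table 1-2:

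- Cohort 1 (12 to < 18 years): AUCtau 9110 ng·h/mL, Cmax 981 ng/mL.
- Cohort 2 (6 to < 12 years): AUCtau 6250 ng·h/mL, Cmax 865 ng/mL.

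**Assumptions.** Kinetics are linear. Half-lives and troughs are assumed, because neither document gives them.

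**Step 1: the identity.** Under linear kinetics, single-dose AUCinf = steady-state AUCtau = F × Dose/CL. The AUC to infinity from a steady-state profile is AUCtau + Ctau/lambda_z. A one-compartment model with first-order absorption (rate constant 1 per hour, arbitrary AUC units) gives:

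| Half-life | Single-dose AUCinf | Steady-state AUCtau | AUC to infinity from steady-state profile |
|---|---|---|---|
| 6 h | 8.656 | 8.656 | 9.309 |
| 12 h | 17.312 | 17.312 | 23.437 |
| 24 h | 34.625 | 34.625 | 70.279 |

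The first two areas agree and the third is larger, so the bias in CL/F is downward. In the same model 99.2% of steady state is reached by Day 7 even at a 24 h half-life (1 − 2^(−168/24)).

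**Step 2: size by half-life.** Ignoring the absorption phase, (Dose/AUCinf from Day 7)/(Dose/AUCtau) = 1 − exp(−k × 24), with k = ln 2/half-life. CL/F is therefore too low by exp(−k × 24):

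| Assumed half-life | CL/F too low by |
|---|---|
| 1 h | 0.0% |
| 3 h | 0.4% |
| 6 h | 6.2% |
| 8 h | 12.5% |
| 12 h | 25.0% |
| 24 h | 50.0% |
| 30 h | 57.4% |

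**Step 3: rough low estimate for GS-331007.** For a one-compartment bolus at steady state, Cmax/Cavg = y/(1 − exp(−y)), where y = k × 24.

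- Cohort 1: 981 × 24/9110 = 2.584, so the half-life is about 7.1 h and CL/F is too low by about 10%.
- Cohort 2: 865 × 24/6250 = 3.322, so the half-life is about 5.2 h and CL/F is too low by about 4%.

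These are effective half-lives. A longer terminal phase would give more.

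**Step 4: size from trough and terminal half-life.** Tail = Ctau × half-life/ln 2, and the understatement is tail/(AUCtau + tail). With a trough of 10% of Cmax and a half-life of 20 h:

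- Cohort 1: tail = 98.1 × 28.85 = 2831; 2831/(9110 + 2831) = 23.7%.
- Cohort 2: tail = 86.5 × 28.85 = 2496; 2496/(6250 + 2496) = 28.5%.

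Across troughs of 5 to 20% of Cmax and half-lives of 10 to 30 h, the extremes are:

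- Lowest: Cohort 1, trough 5%, half-life 10 h. Tail 708; 708/9818 = 7.2%.
- Highest: Cohort 2, trough 20%, half-life 30 h. Tail 7488; 7488/13738 = 54.5%.

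Trough and half-life are linked in practice, so some corners of this grid may be implausible. Steps 3 and 4 together give roughly 4% to 55%.

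**The case against.** The strongest reply is that the formula stands only in a definitions list that looks like template text. The same list defines intravenous clearance and Emax, which no analysis in these documents uses. As a general definition the line is valid, since single-dose AUCinf equals steady-state AUCtau. Neither analysis section directs anyone to extrapolate the Day 7 profile. This stands in part: the documents do not show that CL/F will be computed this way. But no other rule is given and no single-dose profile exists. Either the line is followed and CL/F is biased, or it is not followed and the SAP misstates its method. The same correction serves both cases.

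A reader might infer that GS-331007 clearance is understated by a known, material amount. The documents do not support that. They give no half-life or trough, and the rough estimate from Table 1-2 is far below the top of the range. GS-331007 is also a metabolite formed from SOF (Protocol 1.5), so dose over AUC carries the fraction of SOF converted and is not a plain clearance with either area. Protocol 9.1.2 does list CL/F under both analytes, but Protocol 9.4 and SAP 8.1 qualify what will be reported. The relative error, AUCtau/AUCinf, is the same whatever the numerator is taken to mean.

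A reader might also infer that dose selection is compromised. It is not. Dose confirmation (Protocol 9.4, SAP 8.1) rests on log AUCtau and Cmax of GS-331007. The Cohort 3 scaling in Protocol 1.5 used adult exposures and body-weight relations, not CL/F from this study. The population PK parameters are model-based and reported separately (SAP 8.2).

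**Conclusion.** The point holds as a wrong definition of minor consequence. As written, CL/F has a single-dose formula in a plan that collects only a steady-state profile and lists no AUCinf. Applied to Day 7 data with extrapolation, it would bias CL/F low, and would bias low by the same proportion any volume obtained by dividing that CL/F by lambda_z.

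For SOF the bias is at most 0.4% for half-lives up to 3 h, which is an assumption. For GS-331007 it is roughly 4% to 55% under the assumptions shown, and the documents do not narrow it. Even at the low end the two cohorts differ (about 10% against 4%), so the bias need not cancel in an age comparison. Only the descriptive clearance and volume summaries are affected. No test, endpoint or decision rule uses CL/F.

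**What to change.** In the SAP's pharmacokinetic definitions, replace the formula with steady-state CL/F = Dose/AUCtau and add the matching Vz/F = Dose/(lambda_z × AUCtau); neither document now gives a formula for Vz/F. In SAP 8.1, apply both to the Day 7 parameters for profiles where AUCtau can be estimated. That limit is needed because the intensive PK set requires only one non-missing concentration. State the analytes for which CL/F and Vz/F are reported. If GS-331007 is included, add that the quantity also reflects the fraction of SOF converted.

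The cost is a few lines of SAP text. No new samples or data are needed, and no primary result changes.

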1. INTRODUCTION

This statistical analysis plan (SAP) describes the statistical analysis methods and data presentations to be used in tables, figures, and listings (TFLs) in the clinical study report (CSR) for Study GS-US-334-1112. This SAP is based on the study Protocol Amendment 6 dated 26 February 2016 and the electronic case report form (eCRF). The SAP will be finalized before database finalization. Any changes made after the finalization of the SAP will be documented in the CSR.

